1.1.6. Prior Sodium Pyruvate Treatment in Pulmonary Fibrosis and IPF Studies

A phase 2 study was designed to demonstrate safety, efficacy, and determine which medical endpoints produced clinically and statistically significant results. Inflammatory pathways are upregulated in the nasal epithelium in 80% of patients with IPF, which is part of the etiology of

the disease that effects all lung functions (28). Inflammation induced oxidative stress decreases lung functions including FEV_1 and FVC values and increases mucus and coughing. Nasal steroids and OTC products have been ineffective in treating these conditions in IPF patients, especially when these patients experience exacerbation do to stress or allergies.

Coughing frequency is high in patients with advanced IPF, with median (range) 24-h cough counts varying from 226 (36–946) to 520 (117–1493) depending on the population studied (34-41). In mild to moderate cases in IPF patients, cough counts vary from 4-57 per 24-h. Strikingly, IPF patients experience more cough symptoms during the daytime (median hourly cough rate 14.6 during the day versus 1.9 during the night) (34-41). Chronic cough in IPF is not related to age or gender and is more common in advanced disease and in "never-smokers" (34-41). There is no clear explanation why IPF patients without a history of smoking cough more.

An initial 21-day sub-chronic clinical trial was conducted that included 15 patients with pulmonary fibrosis (9 with pulmonary fibrosis and chronic obstructive pulmonary disease (COPD) and 6 with idiopathic pulmonary fibrosis without COPD) that remained on their normal medications, but were also administered the 20 mM (2.2 mg/mL) sodium pyruvate nasal spray. If the patients were using other nasal sprays as part of their normal therapy, the other nasal spray was eliminated. In all 15 patients, the test results were compared to their previous 3-week screening and baseline data (their current therapies) as the positive control for each variable including all their lung functions, FEV₁, FVC, PEF, FEV₁/FVC ratios, SaO₂, nitric oxide, coughing rates and nasal inflammation (23).

Results

Coughing

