2.1. Primary Objective

Reduce coughing episodes in IPF patients by 25%. (An episode is defined as 5 or more coughs per hour.)

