5.1. Pre-study

Individuals with a clinical diagnosis of idiopathic pulmonary fibrosis (as defined by the WHO and the Thoracic Society) will be solicited for participation in this phase 3 trial. After signing the informed consent, participants will be randomly assigned to either the placebo or drug groups in a double-blinded randomized fashion. On pre-study day 1 (Screening Visit), and, after signing the informed consent, they will have their degree of nasal inflammation and erythema, nasal cellular morphology, SaO₂, and FEV₁, and FVC levels recorded (baseline). All subjects will have a blood sample taken, and women of child-bearing age will provide a urine sample. The subjects will fill out a quality of life questionnaire (chronic respiratory disease questionnaire (CRDQ), and they will be given a data logbook in which they will record the number of coughs they experience each day for 7 days until they return to the clinic to begin the study (baseline). Any subject who is not compliant $\geq 80\%$ will not be entered into the trial.

Blood will be analyzed for CBCs, and for standard clinical variables, including urea nitrogen, serum creatinine, total protein, serum albumin, total globulin, albumin/globulin ratio, total bilirubin, alkaline phosphatase, aspartate aminotransferase (AST or SGOT), Alanine Aminotransferase (ALT or SGPT), Lactate Dehydrogenase (LDH), Gamma-glutamyl Transferase (GGT), Serum Sodium, Potassium, Chloride Serum, Carbon Dioxide, C-reactive protein, and Total Cholesterol:HDL Ratio to determine organ health. Subjects may not enter the study until the blood and urine samples are analyzed and evaluated to confirm that subjects do not have a metabolic abnormality that would prevent entry, and that women are not pregnant.

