The patient population is adult patients \geq 40 years old with mild to moderate IPF with FVC and FEV1 values \geq 50% of predicted values. IPF is defined in accordance with the most recent collaborative guidelines from the American Thoracic Society, the European Respiratory Society, the Japanese Respiratory Society, and the Latin American Thoracic Association (56) including HRCT scan and/or lung biopsy consistent with unusual interstitial pneumonia (UIP), especially honeycombing, without identifiable cause related to other ILD such as drug toxicity, occupational or environmental exposure or connective tissue disease.

The study goal will be to enroll 25 patients with confirmed IPF into the trial in the sodium pyruvate (N115) treatment group and 25 with confirmed IPF to be enrolled in the trial in the placebo group. Efforts will be made to include women and minorities. The study will be a randomized, double-blinded placebo-controlled trial to subjects and study investigators.

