In the case of a subject lost to follow-up, attempts to contact the subject must be made and documented in the subject's medical records.

Withdrawn subjects will not be replaced.

15. A Description of Clinical Procedures, Laboratory Tests, or Other Measures to be Taken to Monitor the Effects of the Drug in Human Subjects and to Minimize Risk

Tests and analyses will be conducted 3 times during the study. If any aberrant values occur, the principal investigator will determine if that patient should continue in the study or be removed. All aberrant values that occur during the study will be considered adverse events. A summary of possible risks will be provided to the patients. Previous risks of using the product are minimal, which included irritation to the nose cavity reported by 1 patient out of 1,869.

16. Safety Precautions Included in this Study

The 0.2% nasal sodium pyruvate inhalation has been administered to both healthy humans and humans with lung diseases, without the occurrence of any SAE.

- First administration of nasal spray on the premises of a hospital/clinic.
- The initial nasal spray will be administered under the supervision of medical staff.
- If a subject develops any adverse event during the follow-up period after study drug administration, the subject will be treated to a satisfactory resolution before being discharged from the clinic.
- Subjects will remain at the test site for monitoring for 30 minutes after the initial inhalation of the nasal spray.
- Follow up telephone communications, as needed.

17. Product Evaluation Questionnaire

This self-administered questionnaire measures the patients' impressions of how the drug affected their nasal cavity, their coughing, and their breathing. It is designed to evaluate changes in a subject's quality of life over time. It will be administered during all clinic visits.

18. Daily Data Logbook

Subjects will use this diary card to record the number of their coughs per day, any self-perceived adverse events, and any medication changes during the study.

19. Urinalysis

Samples will be taken and analyzed to determine if any child-bearing females are pregnant.

20. Study Management

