20.2. Data Collection, Management, and Statistical Analysis

The data management staff at the research clinic will collect and manage the data. Data will be obtained, maintained, and transmitted securely in accordance with HIPAA guidelines. Monitoring and auditing of the data will be conducted by a staff member of Cellular Sciences.

Statistical analysis will be performed on deidentified data. The basic statistical analysis will be repeated measurements of Analysis of Variance using baseline measurements as a covariant (ANCOVA). Age, sex, time since initial diagnosis with IPF, concurrent medications and smoking status are considered potential covariates. Number of coughing episodes reported for a 24-hour pre-study period, and other pre-study data information, will be compared to the data collected during the trial. The differences between baseline data and the data collected during the trial will be compared and analyzed (Within treatment). Additionally, the data of the patients on the experimental therapy will be compared to the data generated by the patients on placebo (Between treatments). P values of <0.5 will be considered significant. FEV1 and FVC will similarly be analyzed as secondary outcome measurements. Relative changes will be analyzed by JMP, Matillion, XLSTAT or R software by [name] or [name], who will be responsible for the statistical analysis.

Partial patient data will be included in the statistical analysis if patients withdraw from the study, but data from non-compliant patients will be excluded. Our previous research (REF) indicates that a sample size of 20 is sufficient to detect a statistically significant difference (p<0.05) between treatment groups. We have chosen to enroll 25 patients in each treatment group to ensure we achieve the necessary sample size, taking into account that some patients may not complete the study, and some data will be incomplete or excluded from the study.

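### The primary objective and the analysis count coughing episodes defined by the hour, but the diary as described records only coughs per day, from which episodes cannot be derived

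*Combined protocol and SAP*

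**What the plan says.** **Unit in the objective and the analysis.** Section 2.1 states the primary objective as a 25% reduction in coughing episodes and adds: "An episode is defined as 5 or more coughs per hour". It does not say what the 25% is measured against, or whether it applies to each patient or to a group. Section 20.2 also works in episodes and compares with trial data the "Number of coughing episodes reported for a 24-hour pre-study period", together with other pre-study information that it does not specify. The model is "repeated measurements of Analysis of Variance using baseline measurements as a covariant (ANCOVA", and differences from baseline are also analysed within each treatment group.

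**Unit in the data collected.** In Section 5.1 patients "record the number of coughs they experience each day for 7 days until they return to the clinic to begin the study (baseline". Section 18 describes the same instrument during the trial: "Subjects will use this diary card to record the number of their coughs per day". Section 5.2 likewise has the daily log record daily coughs, and Section 13 lists daily coughs among the efficacy observations. Section 5.2 also mentions frequency of coughing at the Day 1 visit, without giving a unit or a recording period. The testing schedule in Section 13.1 shows the logbook as the only cough record.

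**Expected cough level.** Section 6.1 enrols adults at least "40 years old with mild to moderate IPF". For mild to moderate disease, Section 1.1.6 says "cough counts vary from 4-57 per 24-h". The same section cites a median of 14.6 coughs per hour by day and 1.9 by night in IPF patients.

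**The concern.** An endpoint defined by what happens within an hour needs data resolved to the hour. The diary as described yields one number per day. If that is all the form records, the variable in the primary objective exists for no patient, before or during treatment. The analyst would then have to substitute another variable, most likely the daily count, without a prespecified rule.

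A smaller question concerns the baseline. Section 20.2 speaks of one 24-hour period without saying which, while Section 5.1 attaches the word baseline to seven daily counts. Nothing says how seven counts become the covariate or the reference for change. With no rule, that choice too could be made after outcome data are seen.

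**Working it through.** The plan states no figure for episodes per day, so there is none to reproduce. The check is whether a daily total fixes the number of episodes.

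**Inputs.** Episode threshold: 5 coughs in an hour (Section 2.1). Hours per day: 24. Background range for mild to moderate IPF: 4 to 57 coughs per 24 hours (Section 1.1.6). Reading adopted: each hour with 5 or more coughs counts as one episode.

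**Bounds for a daily total N.**
- Minimum: up to 4 coughs can fall in every hour without an episode, so the minimum is 0 whenever N <= 4 x 24 = 96.
- Maximum: each episode uses at least 5 coughs and a day has 24 hours, so the maximum is min(24, floor(N/5)).

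| N (coughs per day) | N/5 | Fewest episodes | Most episodes |
|---|---|---|---|
| 4 | 0.8 | 0 | 0 |
| 57 | 11.4 | 0 | 11 |

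The whole 4 to 57 range lies below 96, so every total in it is compatible with no episodes. If each block of 5 coughs within an hour were counted separately, both rows would stay the same.

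**Both ends at 57 coughs can be built.**
- Spread out: 9 hours with 3 coughs and 15 hours with 2 give 27 + 30 = 57 coughs and 0 episodes.
- Clustered: 11 hours with 5 coughs and one hour with 2 give 55 + 2 = 57 coughs and 11 episodes.

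The diary would show 57 for both days.

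**A 25% change does not carry over between the units.**
- Clustered day: if each of the 11 hours falls from 5 coughs to 4, the total becomes 44 + 2 = 46. Coughs fall by 11/57 = 19% and episodes by 100%, from 11 to 0.
- Spread-out day: a 25% fall gives 57 x 0.75 = 42.75, about 43 coughs. Episodes stay at 0.
- Steady rate of 14.6 coughs per hour: a 25% fall gives 14.6 x 0.75 = 10.95 per hour. That is still above 5, so the episode count does not change.

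**Baseline wording side by side.**

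| | Section 20.2 | Section 5.1 |
|---|---|---|
| Unit | episodes | coughs per day |
| Window | one 24-hour period, day not stated | 7 days, labelled baseline |
| Summary for covariate and change | not stated | not stated |

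**The case against.** **The bounds are not likelihoods.** Section 1.1.6 also gives a daytime median of 14.6 coughs per hour, a level at which many daytime hours would be episodes. This stands, and 0 to 11 should not be read as a forecast. It does not rescue the diary, however. At 14.6 per hour, 57 coughs are used up in 57/14.6 = 3.9 hours, so that rate cannot describe a whole daytime for patients in the 4 to 57 range. For patients who cough more, a daily total still does not say how many hours reached 5.

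**The form may record hours.** The diary form was not in the text available, nor were some pages, including the earlier trial's cough results in Section 1.1.6 and the text just before Section 5.1. An hourly form would remove the unit problem. The sections that describe the diary speak only of daily numbers, so the conclusion is about the diary as described.

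**The 24-hour wording may be loose.** Section 1.1.6 uses coughs per 24 hours as an ordinary rate, and the other pre-study information in Section 20.2 may include the diary. This is a fair reading. It turns the window question into a missing specification rather than a firm contradiction. It supplies neither a summary of the seven days nor a change of unit.

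**A zero baseline need not be fatal.** A reader might infer that patients with no baseline episodes make the endpoint undefined. That holds only if the 25% is a per-patient change. Section 20.2 refers to relative changes but does not say per patient, and Section 2.1 would also allow a group-level reduction or one against placebo.

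**Conclusion.** The unit mismatch holds. The primary objective and the analysis are in hourly episodes, while the collection as described is in coughs per day. One cannot be computed from the other at baseline or at follow-up. At 57 coughs per day the episode count is undetermined between 0 and 11; at 4 it is 0. This uses the protocol's own definition and background range and needs no assumption about variance. It depends on the diary form recording no hours.

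The baseline window is a secondary point: the 24-hour and 7-day wordings should be reconciled and one summary named.

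Three stronger inferences are not supported:
- **Bias.** Either baseline window leaves the randomised comparison unbiased.
- **Precision.** The documents give no day-to-day correlation of cough counts. Whether a 7-day mean does better or worse than a single day depends on the correlation pattern assumed, so no gain is claimed.
- **The Day 1 record.** Nothing in the documents rules out the pre-dose Day 1 cough record as a baseline. The plan just does not say what that record is or how it is used.

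**What to change.** **Use one cough unit in Sections 2.1, 5.1, 18 and 20.2.** There are two routes.

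1. *Coughs per day.* Restate the objective in Section 2.1 and the analysis in Section 20.2 in the unit that the diary already collects. No new data are needed. The cost is a reworded primary objective: the 25% target must be reaffirmed in coughs, because it does not carry over from episodes. Settle this before enrolment, or at the latest before any outcome data are seen.
2. *Episodes.* Change the diary form before enrolment so that it captures hourly counts or episodes, from the pre-study week onward. The cost is a new form and more recording by patients. If the 25% is a per-patient change, also state how a zero baseline is handled.

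If the existing form already records hours, say so in Sections 5.1 and 18 and give the rule for deriving episodes.

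**In the same edit, define baseline cough once in Section 20.2**, for use both as the ANCOVA covariate and as the reference for change. The mean of the available pre-study diary days is a natural choice because Section 5.1 already calls the diary the baseline. Another summary fixed in advance would also meet the point. State what the Day 1 cough record is and whether it enters the baseline. This part costs a few sentences.

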Clinically, sodium pyruvate has been given to patients for a variety of disorders ranging from Friedreich's ataxia (20) to open heart operations. It has been administered via several routes including intravenous (10-20 times our inhaled therapeutic dose) (21-27,30), topical administration for hyperkeratotic disorders, and in dietary supplementation. Sodium pyruvate has been shown to protect neurons, lungs, hearts, muscles, cerebral metabolism, embryos, eyes, kidneys, cellular DNA and membranes from oxygen radical damage (13-18, 20-27). The levels of pyruvate in these studies were 2-32 mM. In human and animal studies, pyruvate was shown to facilitate wound healing, decrease inflammation, and decrease production of oxygen radicals (20-27). It is being sold as an OTC product and is a constituent in a therapeutic solution used in

open heart surgery, kidney surgery, eye surgery, for hyperkeratotic disorders, to treat mitochondrial diseases, in organ transplant media that is being used to preserve human lungs, hearts, and other organs for human transplants. These transplant media contain sodium pyruvate ranging from 10 mM to 32 mM to keep the organs safe and functional for longer periods of time. There were no safety concerns for this compound.

Based on results from clinical research, it seems reasonable to treat patients with IPF with a sodium pyruvate nasal spray, which is shown to reduce inflammation, increase FEV_1 and FVC and values, and decrease coughing and other nasal symptoms.

2. Purpose and Objectives of the Studies

The purpose of this clinical trial is to administer a sodium pyruvate nasal spray that eliminates nasal oxidative stresses, caused by oxygen radicals, and demonstrate the efficacy of sodium pyruvate to reduce coughing and increase lung functions.

This will be a 21-day double-blinded randomized placebo-controlled trial designed to determine if patients with idiopathic pulmonary fibrosis treated with 0.2% sodium pyruvate (2.1 mg/mL) in 0.9% sodium chloride nasal spray solution will:

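### The 25% cough target has no stated reference, and the plan does not say whether the within-arm or the placebo comparison decides, so success could be claimed from the N115 arm alone

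*Combined protocol and SAP*

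**What the plan says.** Section 2 opens by describing a randomised, double-blind study with a placebo control, said to be "designed to determine if patients with idiopathic pulmonary fibrosis treated with 0.2% sodium pyruvate (2.1 mg/mL) in 0.9% sodium chloride nasal spray solution will" achieve the listed objectives. The primary one, in Section 2.1, is: "Reduce coughing episodes in IPF patients by 25%. (An episode is defined as 5 or more coughs per hour". Neither the patient's own baseline nor placebo is given as the reference.

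Section 20.2 describes the analysis in this order:

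- The model: "The basic statistical analysis will be repeated measurements of Analysis of Variance using baseline measurements as a covariant (ANCOVA". No treatment term, contrast or time point is named.
- The only sentence that mentions coughing episodes sets pre-study data against on-trial data: "Number of coughing episodes reported for a 24-hour pre-study period, and other pre-study data information, will be compared".
- The first labelled comparison: "The differences between baseline data and the data collected during the trial will be compared and analyzed (Within treatment".
- The second labelled comparison: "Additionally, the data of the patients on the experimental therapy will be compared to the data generated by the patients on placebo (Between treatments".
- One decision rule, not limited to either comparison: "P values of <0.5 will be considered significant".

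The sample-size statement in the same section says that 20 patients suffice for a significant difference (p<0.05) between the arms. It plans 25 per arm to allow for losses.

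**The concern.** A before/after change in one arm combines any drug effect with everything else that moves cough counts over three weeks. Several such influences act on both arms here. Patients count their own coughs in a diary (Sections 5.1 and 18) and are telephoned every two days (Section 5.2). The placebo is itself a saline spray (Section 3). Corticosteroids, antihistamines and rescue medication are permitted (Section 11). Only the randomised contrast removes a change that both arms share.

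With the reference for the 25% undefined and no deciding contrast named, a report that N115 patients fell by 25%, significantly against baseline, would be consistent with the plan even if placebo patients fell as much. Reading before/after change as efficacy is also how much of the supporting work is presented. The 21-day pulmonary fibrosis study used patients' own earlier data as its control (Section 1.1.6). The long-COVID study compared an untreated week with a treated week (Section 1.1.8). Once the data have been seen, a choice between the two contrasts is no longer credible.

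**Working it through.** **1. The plan's own figure.** The stated n of 20 cannot be reproduced, because no effect size, SD or power is given and the cited source is an unfilled reference. Solving backwards, reading 20 as per arm, with two-sided 0.05 and the normal approximation: detectable standardised difference = (1.960 + 0.842) × √(2/20) = 0.886 at 80% power, or 1.025 at 90%. The step from 20 to 25 fits a 20% loss, 20/(1 − 0.20) = 25, but that rate is inferred. This statement concerns the between-arm contrast and does not address a within-arm test.

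**2. Inputs for the check.**
- From the plan: 25 per arm (Section 6.1); significance level 0.05 (the sample-size statement in Section 20.2, not the printed 0.5).
- Assumed, because the documents give neither: a true fall shared by both arms of 10% or 20% with no drug effect, and an SD of log change of 0.4 to 0.6.

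**3. Within-arm test in N115.** One-sample t-test on log change, 24 df, critical value 2.064, noncentrality = −ln(1 − fall) × √25 / SD.
- Shared 10% fall: 0.1054 × 5 / 0.4 = 1.317 and 0.1054 × 5 / 0.6 = 0.878.
- Shared 20% fall: 0.2231 × 5 / 0.4 = 2.789 and 0.2231 × 5 / 0.6 = 1.860.

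**4. Observed (geometric mean) fall of at least 25% in N115.** z = [−ln(0.75) + ln(1 − fall)] / (SD/√25), with −ln(0.75) = 0.2877.
- Shared 10% fall: 0.1823/0.08 = 2.279 and 0.1823/0.12 = 1.519.
- Shared 20% fall: 0.0645/0.08 = 0.807 and 0.0645/0.12 = 0.538.

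| Shared fall, no drug effect | SD of log change | Within-arm p<0.05 | Observed fall ≥25% |
|---|---|---|---|
| 10% | 0.4 | 24% | 1% |
| 10% | 0.6 | 13% | 6% |
| 20% | 0.4 | 76% | 21% |
| 20% | 0.6 | 43% | 30% |

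**5. Second scale.** With percent change, an assumed SD of 30 to 50 points and 25 per arm, within-arm significance in favour of N115 occurs in 16–36% of trials at a shared 10% fall and 48–89% at 20%. A mean fall of at least 25% occurs in 0.6–7% and 20–31%. The pattern does not depend on the log scale.

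**6. Between-arm test, same scenarios.** The shared fall cancels. In 100,000 simulated trials per scenario on the percent-change scale, a two-sided 0.05 test was positive in 5%, with 2.5% in favour of N115, whatever the shared fall. At the printed threshold of 0.5 it was positive in 50%.

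**7. What a placebo-relative target would demand.** Power for a true N115/placebo ratio of 0.75: noncentrality = 0.2877 / (SD × √(2/25)), 48 df, critical value 2.011. For SD 0.4, 0.5 and 0.6 this is 2.543, 2.034 and 1.695, giving power of 70%, 51% and 38% before any gain from baseline adjustment.

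**The case against.** The design points to a placebo comparison. The objective follows from a sentence describing a placebo-controlled trial. The first analysis named in Section 20.2 is a baseline-adjusted ANCOVA, which is normally used to compare randomised groups. A between-treatment comparison is expressly planned, and the sample-size statement refers to it. All of this stands, and it rules out four stronger readings that a reader might draw:

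- *The 25% is defined within the arm.* It is not; its reference is simply missing.
- *The placebo comparison is absent or the control arm is discarded.* It is planned.
- *The word* additionally *makes it secondary.* That word gives an order of mention, not a rank.
- *A within-arm result meets the plan's success rule.* There is no success rule; the plan leaves such a claim open.

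These points show intent but do not settle which result decides. The ANCOVA sentence names no contrast, and sizing a trial for a contrast does not designate it primary.

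Two further objections also stand. The size of the problem depends on an undocumented shared fall and is much smaller at 10% than at 20%. Regression to the mean is a weak argument here, since Section 6.2 asks only for a condition-related cough and sets no minimum count.

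**Conclusion.** The point holds as an undefined reference for the 25% and an undesignated deciding contrast. It should be settled before any outcome data are seen, because it determines what counts as success on the primary endpoint of a phase 3 trial.

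With no drug effect, a within-arm test favours N115 in 13–24% of trials at a shared 10% fall and 43–76% at 20%, against 2.5% for a between-arm test at two-sided 0.05. Relying on the observed 25% fall alone is a small risk at a shared 10% (1–6%) and a large one at 20% (21–30%).

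These figures rest on assumed falls and SDs and on reading the threshold as 0.05. They also treat patient-level change as computable, which may fail for some patients. Section 1.1.6 gives 4–57 coughs per 24 hours in mild to moderate disease, the population enrolled under Section 6.1. A patient with 4 coughs in a day cannot have an hour with 5, so days with zero episodes are possible.

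**What to change.** - **Section 20.2:** name the N115-versus-placebo treatment effect from the baseline-adjusted repeated-measures model, at a stated time point or over a stated period, as the single primary analysis, reported with a 95% confidence interval. Reconcile the printed 0.5 with the 0.05 in the sample-size statement; without this the between-arm test does not hold 5%.
- **Section 2.1:** state the 25% as relative to placebo, on a scale that handles days with zero episodes. A ratio of the arms' mean episode rates over the chosen period is one option, since it needs no logarithm of individual counts.
- **Within-arm changes:** descriptive only, without p-values and not a basis for an efficacy claim.

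This changes text only and needs no new data, but it is not free. The criterion becomes stricter, and under the assumed SDs power for a ratio of 0.75 is only about 38–70% at 25 per arm before any gain from baseline adjustment. The 25% should therefore be presented as a target effect to be estimated, not as a threshold that the trial has been shown to be powered for.
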